
**Blood sampling and analysis:** Blood samples will be collected through venipuncture of an arm vein into heparin, ethylenediaminetetraacetic acid (EDTA), or serum separator Vacutainers $\text{R}$  in the seated upright position prior to heating (baseline) and at the point of

thermal tolerance (end). We will measure hematocrit (microcapillary technique) and hemoglobin (ABL90 Flex, Radiometer, Brønshøj, Denmark) to calculate changes in plasma volume (Dill & Costill, 1974). Blood samples will be centrifuged to isolate plasma/serum and aliquots stored at -80°C for later analyses. We will measure plasma (heparin) intestinal fatty acid binding protein (I-FABP), plasma (EDTA) lipopolysaccharide binding protein (LBP), and plasma (EDTA) soluble cluster of differentiation 14 (sCD14) using enzyme-linked immunosorbent assays. In addition, to assess changes in renal function we will measure plasma (heparin) creatinine (Medica RA chemistry analyzer) and cystatin C (Tosoh AIA-360). Stored serum samples will be assayed using a chemo/cytokine multiplex assay (LHC0009M ThermoFisher Scientific, Waltham, MA) run on a Luminex™ MAGPIX platform (xMAP Technology, San Diego, CA).

**Urine analysis:** Stored urine samples will be assayed for tissue inhibitor of metalloproteinase 2 (TIMP-2) insulin like growth factor binding protein 7 (IGFBP7), neutrophil gelatinase-associated lipocalin (NGAL), and kidney injury molecule-1 (KIM-1) via enzyme-linked immunosorbent assays (RayBiotech Life, Peachtree Corners, GA). Urinary biomarkers will be normalized to urine flow rate.

**Multi sugar drink:** Intestinal permeability will be assessed using a multi sugar drink test as described elsewhere (van Wijck *et al.*, 2013). The drink will be modified to include only 1 g of lactulose (Kristalose®, Cumberland Pharmaceuticals, Nashville, TN), 1 g of sucrose (107653, Sigma-Aldrich, St. Louis, MO), and 0.5 g of L-rhamnose (W373011, Sigma-Aldrich, St. Louis, MO). The urinary recovery of each ingested sugar (lactulose, sucrose and rhamnose) will be determined by multiplying the measured concentration of each sugar by the total volume of urine collected and dividing by the dose administered. If lactulose or sucrose is not detected in the sample, the L/R ratio or sucrose excretion will be assumed to be 0.

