Impact of Aging on Gastrointestinal Permeability During Hyperthermia

Statistical Analysis Plan

NCT05816551

October 7, 2024

Statistical Analysis Plan: Data will be assessed for model assumptions (i.e., normality, equality of variance) and inspected for influential data points. Non-normally distributed data will be transformed using a log base 10 transformation. Data will be analyzed using linear mixed effect models with main effects of time or trial (within factor) and group (between factor; older vs young) or unpaired t-tests, as appropriate. Statistical significance was set a priori to $p < 0.05$.

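### In the supplied text no outcome or contrast is primary, and one p < 0.05 rule covers 11 named outcomes plus a cytokine panel, so a finding picked from this set does not carry a 5% error rate

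*SAP*

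**What the plan says.** The SAP is a single paragraph. After assumption checks and a log base 10 transformation for non-normal data, it specifies mixed models with "main effects of time or trial (within factor) and group (between factor; older vs young) or unpaired t-tests, as appropriate". It closes with one threshold: "Statistical significance was set a priori to" p < 0.05. It mentions no primary outcome, ranking of outcomes or adjustment for multiple tests, and it does not describe the study as exploratory.

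The outcomes are in the protocol:

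- **Multi sugar drink:** L/R ratio and sucrose excretion. For samples in which lactulose or sucrose is undetected, "the L/R ratio or sucrose excretion will be assumed to be 0".
- **Blood sampling and analysis:** "plasma (heparin) intestinal fatty acid binding protein (I-FABP), plasma (EDTA) lipopolysaccharide binding protein (LBP), and plasma (EDTA) soluble cluster of differentiation 14 (sCD14"); then, for the kidney, "plasma (heparin) creatinine (Medica RA chemistry analyzer) and cystatin C (Tosoh AIA-360").
- **Blood sampling and analysis, serum:** "Stored serum samples will be assayed using a chemo/cytokine multiplex assay". The number of analytes is not given.
- **Urine analysis:** "Stored urine samples will be assayed for tissue inhibitor of metalloproteinase 2 (TIMP-2"), with IGFBP7, NGAL and KIM-1.

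**The concern.** The study title asks how ageing affects gastrointestinal permeability during hyperthermia. Under the rule as written, the permeability measures have no higher standing than six kidney markers or any single cytokine. A kidney marker or cytokine with p = 0.04 could carry the conclusion about ageing while the L/R ratio showed nothing, and the plan would not mark that as a selected result.

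The contrast is open as well. The SAP names main effects only. A group main effect averages the age difference over both levels of the within-person factor. The titled question is whether the response to heat differs by age, which is an interaction.

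**Working it through.** The documents state no family-wise error rate, sample size or power, so there is no figure of the plan's own to reproduce. The only numerical input is the 0.05 threshold.

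**Inputs**

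- Per-test level: 0.05 (SAP). Sidedness is not stated; two-sided is assumed.
- Named outcomes: 2 permeability (L/R ratio, sucrose excretion) + 3 gut-barrier or translocation markers (I-FABP, LBP, sCD14) + 2 renal blood markers (creatinine, cystatin C) + 4 urinary kidney markers (TIMP-2, IGFBP7, NGAL, KIM-1) = 11.
- Cytokines: count not given; 10 to 25 is an assumed range, giving 21 to 36 outcomes in all.
- Tests counted: one per outcome, the older-versus-young comparison. Heat tests are left out because heating probably does change some markers.

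**Independent tests, no true age difference in any marker**

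P(at least one p < 0.05) = 1 − 0.95^m

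- m = 11: 1 − 0.569 = 43%
- m = 21: 1 − 0.341 = 66%
- m = 36: 1 − 0.158 = 84%

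**Correlated tests**

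The test statistics are taken as normal with a common correlation ρ. Given the shared component g, each test stays below c = 1.96 in absolute value with probability

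h(g) = Φ((c − √ρ·g)/√(1−ρ)) − Φ((−c − √ρ·g)/√(1−ρ)),

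and the chance of at least one false positive is 1 − E[h(g)^m], with g standard normal. Numerical integration gives:

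| Outcomes tested | ρ = 0 | ρ = 0.3 | ρ = 0.5 | ρ = 0.8 |
|---|---|---|---|---|
| 11 (named) | 43% | 37% | 30% | 18% |
| 21 (plus 10 cytokines) | 66% | 55% | 43% | 23% |
| 36 (plus 25 cytokines) | 84% | 72% | 55% | 27% |

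A simulation of 200,000 draws agrees for 11 and 21 outcomes to within 0.3 percentage points.

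**Narrower families, independent tests**

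- Two permeability outcomes: 1 − 0.95² = 9.8%
- Those two plus I-FABP, LBP and sCD14: 1 − 0.95⁵ = 22.6%

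**Check of the remedy**

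One named outcome with one named contrast at 0.05 has a 5% error rate for that claim. For comparison, Bonferroni over the 11 named outcomes tests each at 0.05/11 = 0.00455, and 1 − (1 − 0.00455)^11 = 4.9%.

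**Can the proposed primary be analysed as the plan stands?**

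The protocol sets the L/R ratio to 0 when lactulose is undetected. The SAP log10-transforms data that are not normal. Log10 of 0 is undefined, so the two instructions conflict in any sample without detectable lactulose.

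**The case against.** The case against has five parts.

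1. **The supplied text is incomplete.** Some pages were removed before review, and the registry record was not available. A primary outcome may be recorded there. This stands, and the point is limited to the supplied text. Likewise, the SAP is silent on adjustment; it does not rule it out.

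2. **The larger percentages are worst cases.** A reader might infer that a false age or heat finding is close to a coin toss, or more likely than not. Counting age and heat tests on 11 outcomes gives 68% if independent (1 − 0.95^22) and about 52% at a correlation of 0.5. But that treats every heat test as a true null, in a study that heats participants by up to 2°C. Independence is doubtful too: the four urinary kidney markers come from the same samples and share a normalisation to urine flow rate. A figure of 82% (1 − 0.95^33) would need three tested effects per outcome, and the SAP names only two. The documents do not support these stronger readings.

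3. **The family is too wide.** The protocol gives the renal blood markers their own purpose, and the permeability question alone involves two to five outcomes. This is fair and lowers the figure to between 9.8% and 22.6% if independent. But the SAP does not divide the outcomes into families, and even the narrowest reading is about twice 5%.

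4. **Exploratory physiology studies need no formal control.** That is a legitimate choice, but neither document makes it.

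5. **It may be too late.** The SAP is dated October 2024 and partly in the past tense. If results had already been seen, naming a primary now would not restore a prespecified 5%. The documents do not settle this, so the fix must cover it.

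**Conclusion.** The concern holds for the protocol and SAP as supplied. A single 0.05 rule over 11 named outcomes and a cytokine panel, with nothing designated primary, does not give a 5% error rate to a conclusion chosen from that set. For the age comparison on the 11 named outcomes, the chance of at least one false positive lies between about 18% and 43%, depending on correlation. With the panel added, it lies between about 23% and 84%.

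These figures assume that no marker truly differs by age, that all markers share one common correlation between 0 and 0.8, that each outcome contributes one two-sided test, and that the panel has 10 to 25 analytes. True age differences in some markers would reduce them. This should be corrected, but it does not invalidate the data or the design.

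**What to change.** Change the SAP as follows.

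- **Primary outcome and contrast.** Designate the urinary L/R ratio as the single primary outcome, or carry over the primary already recorded elsewhere if there is one. Its contrast is the group-by-trial interaction: older versus young in the change from control visit to hyperthermia trial, tested at 0.05.
- **Model.** Add that interaction to the mixed model, which at present lists main effects only.
- **Zeros.** State a method for L/R values of 0 that does not rely on log10 of 0. One option is a permutation or rank comparison of within-person changes on the untransformed scale; another is to treat undetected values as censored at the assay limit.
- **Other outcomes.** Apply Benjamini-Hochberg or Holm within the cytokine panel and, separately, within the other biomarkers. Label any unadjusted result exploratory.
- **Timing.** If data had already been analysed when the primary was chosen, say that the designation is post hoc.

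This takes a few sentences and no new data or participants. The downside is that some secondary markers and cytokines with p just below 0.05 will no longer be called significant. The supplied text gives no sample size, so the power of the interaction test cannot be judged from it.
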